### **6.1.2. Definition of Study Baseline**

Unless otherwise specified, for all measurements, baseline is defined as the last nonmissing assessment recorded on, or prior to, the date of the study drug administration at study Day 1.

Baseline SARS-CoV-2 RT-PCR and serology status will be based on evaluable test results on, or prior to, the date of study drug administration at study Day 1. A participant will be considered RT-PCR positive at baseline if any RT-PCR result is determined to be positive.

Baseline for safety analysis is described in the safety section.

Change from baseline will be calculated as the visit value of interest minus the baseline value. If a baseline value or the value at the visit is missing for a particular variable, then the change from baseline is defined as missing.

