Vital signs	X	Daily										X	X	X		Documentation of hospital-based exam is acceptable. Includes: body temperature, pulse rate, BP, SpO ₂ , respiratory rate, FiO ₂ if known, and method of delivery, if applicable. Record while participant is at rest.

Procedures	Screening	Evaluation Period										ETV	Post-Evaluation Follow-Up			Comments
Study Day	Max 7-day window	1	2-7	8	15	22	29	36	43	50	57		85	141	169	
Visit window (\pm number of days)	--	--	--	2	2	2	2	2	2	2	2		7	7	7	
Hospitalization events		Daily										X	X	X		Record if the following events occur: 
Emergency room visitshospitalizedICU admittance,Extended care facility admittance,and discharge for any of the above
Clinical status and concomitant procedures of special interest in hospitalized participants		Daily										X	X	X		Documentation from hospital records is acceptable. Includes: consciousness status (ACVPU), limitation on activities due to COVID-19, and requirements for 
Ongoing hospital medical careSupplemental oxygennon-invasive ventilation or a high flow oxygen devicemechanical ventilationextracorporeal membrane oxygenation, oradditional organ support (e.g. pressors, renal replacement)
Clinical symptoms and interventions of interest		Daily										X	X			See Table 1 for clinical symptoms and interventions of interest.

Procedures	Screening	Evaluation Period										ETV	Post-Evaluation Follow-Up			Comments
Study Day	Max 7-day window	1	2-7	8	15	22	29	36	43	50	57		85	141	169	
Visit window (\pm number of days)	--	--	--	2	2	2	2	2	2	2	2		7	7	7	
Symptoms Questionnaire	X	Daily										X	X		See Section 8.1.2.	
SARS-CoV-2 POC Test (Nasal Swab)	X														Applies to participants in Part 2 only. Result must be determined prior to collecting swabs for PCR test.	
SARS-CoV-2 Serology		X				X			X	X	X	X	X	X	Day 1: pre-dose. assessed at a central laboratory	
SARS-CoV-2 nasopharyngeal swab (for PCR test) taken from both nostrils		X													Day 1: pre-dose. assessed at a central laboratory	
SARS-CoV-2 nasal swab (for PCR test) taken from both nostrils		X		X	X	X	X	X	X	X	X	X	X		Day 1: pre-dose. assessed at a central laboratory No samples needed if participant is hospitalized.*	

Procedures	Screening	Evaluation Period										ETV	Post-Evaluation Follow-Up			Comments
Study Day	Max 7-day window	1	2-7	8	15	22	29	36	43	50	57		85	141	169	
Visit window (\pm number of days)	--	--	--	2	2	2	2	2	2	2	2		7	7	7	

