Additional manageable risks associated with most therapeutic monoclonal antibodies are the potential for infusion-related hypersensitivity and cytokine release reactions. The single infusion in this study will be administered at a controlled rate, the study participants will be monitored closely, and adjustments in the infusion rate will be made and/or the infusion stopped, if indicated. Additional information regarding infusion reaction management options is located in Section 6.1.1.2. As of 31 December 2020, approximately 4012 participants received blinded treatment of LY3819253 700 mg, 2800 mg, or 7000 mg, or placebo, of which approximately 3189 participants received LY3819253. Serious infusion-related reactions, including events consistent with anaphylaxis, were reported in these ongoing studies with LY3819253 (FDA EUA fact sheet 2020).

Clinical worsening of COVID-19 after administration of LY3819253 has been reported from post-authorization treatment within 24 hours of infusion. Signs and symptoms may include fever, hypoxia or increased respiratory difficulty, arrhythmia (e.g., atrial fibrillation, sinus tachycardia, and bradycardia), fatigue, and altered mental status. Some of these events required hospitalization. It is not known if these events were related to LY3819253 use or were due to progression of COVID-19.

Combination of LY3819253 and LY3832479

As of 04 November 2020, 542 participants in Study PYAB received blinded treatment of either placebo or the combination of 2800 mg LY3819253 and 2800 mg LY3832479. Three participants reported single immediate non-serious events of pruritis (2 events) and dyspnea (1 event).

Data from Study PYAB interim analysis indicate treatment with LY3819253 or the combination of LY3819253 and LY3832479 may decrease the risk of hospitalization in patients with mild to moderate COVID-19 (Chen et al. 2020; Gottlieb et al. 2020) thus providing benefit to patients with COVID-19.

Given the totality of data on LY3819253 and LY3832479, the well-established safety profile of other therapeutic mAbs, and the lack of disease directed therapeutic options for patients with COVID-19 illness or to prevent the SARS-CoV-2 infection, the overall benefit/risk assessment of this study is considered favorable.

More detailed information about the known and expected benefits and risks and reasonably expected adverse events of LY3819253 and LY3832479 may be found in each respective IB.

3. Objectives and Endpoints

Part 1

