9.4.1. General Considerations

Baseline values for all measurements will be the last measurement taking prior to receiving study intervention, unless otherwise specified.

The primary analyses of the primary endpoints and key secondary endpoints will be based on events that occurred after randomization.

The analysis model for time-to-event analyses will be a Cox proportional hazards regression model for the time to the first occurrence of the relevant event, with treatment as a fixed effect. For continuous measures, analysis of covariance (ANCOVA) and/or mixed-effects model for repeated measures (MMRM) will be used to analyze changes from baseline with the baseline

value as the covariate. The MMRM model will include fixed effects for treatment, visit, treatment-by-visit interaction, the baseline as a covariate and the participant as a random effect. Summary statistics will include sample size, mean, standard deviation, median, 10th and 90th percentiles for both the actual and the change from baseline measurements. Least-squares mean (LS mean) and standard error derived from the model will also be displayed for the change from baseline measurement. Treatment comparisons will be displayed showing the treatment difference LS Mean and the 95% confidence limits along with the p-value.

For continuous lab measurements, an analysis of variance (ANOVA) on ranks will be used and p-values for the difference between each study intervention and placebo will be reported.

For categorical measures, summary statistics will include sample size, frequency, and percentage. For primary and secondary analyses, a logistic regression model will be used. The model will include fixed effects for treatment and stratification factors such as facility. For other analyses, frequencies will be analyzed using Chi-square tests if the expected count is at least 5, in at least 80% of the cells, otherwise a Fisher's exact Test will be used.

All analyses will be implemented using SAS[®] Version 9.4 or higher, or R version 3.6.3 or higher.

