### ***6.10.3. Secondary Efficacy Analyses***

#### **6.10.3.1. Incidence of Moderate-or-Worse Severity COVID-19 by Day 57**

As a key secondary endpoint, the proportion of patients in the Prevention populations who develop moderate-or-worse severity COVID-19 (defined as the detection of SARS-CoV-2 by polymerase chain reaction (RT-PCR) AND moderate or worse disease severity within 21 days of detection) by Day 57 will be summarized by treatment group. Similar methodology, as described in Section 6.10.1 will be utilized for statistical hypothesis testing, following the testing scheme described in Section 6.5.

As a sensitivity assessment, participants who develop COVID-19 within 21 days of becoming SARS-CoV-2 positive by RT-PCR, then continue on to develop moderate-or-worse disease severity by Day 57, will be included as moderate-or-worse severity COVID-19 events in the assessment.

As an exploratory analysis, the incidence of moderate-or-worse severity COVID-19 within 21 days of randomization will be compared across treatment groups in the subset of participants in the Treatment populations who did not have moderate-or-worse severity COVID-19 at baseline. Statistical comparisons will use similar methodology as described in Section 6.10.1.

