### 6.12.1. Baseline and Postbaseline Definitions for Safety Groups

Table PYAD.6.7 provides conceptual definitions of baseline and postbaseline by analysis type. More specific detail for each submission is provided in an appendix, if necessary.

**Table PYAD.6.7. Baseline and Postbaseline Definitions for Safety Groups  
Initial Controlled Periods of Individual Studies  
Controlled Integrated Analysis Sets**

Analysis Type	Baseline	Postbaseline
TEAEs	Start of screening and ends prior to the study drug dose.	Starts after initiation of the study drug dose and ends on or prior to the day of study disposition
Treatment-Emergent Abnormal Laboratory Values and Vital Signs	Start of screening and ends prior to the study drug dose.  All scheduled and unscheduled measurements will be included.	Starts after initiation of the study drug dose and ends on or prior to the day of study disposition.  All scheduled and unscheduled measurements will be included.

**Baseline and Postbaseline Definitions for Safety Groups****Initial Controlled Periods of Individual Studies****Controlled Integrated Analysis Sets**

Analysis Type	Baseline	Postbaseline
Change from Last Baseline to Week xx and to Last Postbaseline for Laboratory Values and Vital Signs	Start of screening and ends prior to the study drug dose.  The last scheduled nonmissing assessment recorded prior to the date of the first dose.	Starts after initiation of the study drug dose and ends on or prior to the day of study disposition.
		Only scheduled visits will be included. The early termination visits are considered scheduled visits.

Abbreviation: TEAE = treatment-emergent adverse event.

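### SAP 6.1.2 sets the general baseline by dosing date where protocol 9.4.1 sets it before dosing, so a Day 1 post-infusion value can become baseline in a few exploratory efficacy analyses

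*SAP*

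**What the plan says.** The general rule in SAP 6.1.2 is that "baseline is defined as the last nonmissing assessment recorded on, or prior to, the date of the study drug administration at study Day 1". The test is the calendar date; clock time plays no part. Infection status follows the same pattern: "Baseline SARS-CoV-2 RT-PCR and serology status will be based on evaluable test results on, or prior to, the date of study drug administration". Safety is carved out: "Baseline for safety analysis is described in the safety section", and Table PYAD.6.7 gives that baseline window as "Start of screening and ends prior to the study drug dose".

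Protocol 9.4.1 reads differently: "Baseline values for all measurements will be the last measurement taking prior to receiving study intervention, unless otherwise specified". Protocol 9.4 expects a change from its analysis methods to be described and justified in the SAP; SAP 6.1.2 gives no reason for this one. SAP Table PYAD.6.2 starts the Evaluation Period at the date and time of dosing.

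In the protocol's Schedule of Activities (1.3), Day 1 swabs and serology are marked "Day 1: pre-dose. assessed at a central laboratory", and hematology, chemistry, antidrug-antibody and biomarker samples are also marked pre-dose. Vital signs, the symptoms questionnaire, clinical symptoms and hospitalization events carry no such mark. SAP Appendix 1 takes the NIAID score for a day as the lowest reached that day.

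Three exploratory analyses depend on baseline clinical status:
- COVID-19 incidence in Treatment-population participants asymptomatic at baseline (SAP 6.10.1);
- moderate-or-worse incidence "in the subset of participants in the Treatment populations who did not have moderate-or-worse severity COVID-19 at baseline" (SAP 6.10.3.1);
- any NIAID worsening from baseline (SAP 6.16.2.2).

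**The concern.** Read literally, the SAP lets a reading taken hours after the infusion define the state from which deterioration is measured. A participant who develops symptoms that afternoon could be classed as symptomatic at baseline and drop out of the subset meant to detect exactly that change. Under Table PYAD.6.2 the same reading already belongs to the Evaluation Period, so it would be baseline and outcome at once.

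The first day matters in this trial. Protocol 2.3 states: "Clinical worsening of COVID-19 after administration of LY3819253 has been reported from post-authorization treatment within 24 hours of infusion". The infusion-reaction symptoms listed in protocol 6.1.1.2 (fever, headache, nausea, myalgia) also overlap the mild COVID-19 symptoms in protocol Table 1, so a reaction alone could change a participant's apparent baseline status. If such events were more frequent on active drug than on placebo, removing them would flatter the active arm.

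**Working it through.** **Design figures.** The plan gives no figure for this point. Its 33 events for Part 1 do not use the baseline definition. Schoenfeld's formula with two-sided 0.05, 90% power and 1:1 allocation gives 4(1.960 + 1.282)²/(ln 0.33)² = 34.2. With the hazard ratio implied by 4.0% against 1.32%, ln(1 − 0.0132)/ln(1 − 0.04) = 0.3255, it gives 33.4. Both are close to 33, and the baseline rule changes neither.

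**The rules side by side.**

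| Place | Cut-off | Can a Day 1 post-infusion value be baseline? |
|---|---|---|
| Protocol 9.4.1 | before the intervention | no |
| SAP 6.1.2, general | dosing date | yes |
| SAP 6.1.2, RT-PCR and serology | dosing date | not for scheduled samples, which are pre-dose |
| SAP Table PYAD.6.2 | date and time of dosing | no; it falls in the Evaluation Period |
| SAP Table PYAD.6.7, safety | before the dose | no |

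**What is reached.** The Prevention populations are defined by RT-PCR and serology (and the point-of-care test in Part 2). Symptoms and vital signs therefore cannot remove anyone from the primary or key secondary analyses. Hospitalization or death (SAP 6.10.3.4) and deterioration (6.10.3.5) have no baseline-severity restriction. That leaves the three exploratory analyses.

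**Two constructed cases.**
- An RT-PCR-positive participant has no symptoms before the infusion, then fever and headache recorded later on Day 1. Protocol rule: at risk, with an event. SAP rule: not asymptomatic at baseline, so outside the 6.10.1 subset.
- A participant scores 8 on the NIAID scale before the infusion, is admitted that evening with a score of 5, and never scores lower. Protocol rule: worsened. SAP rule: baseline 5, so not worsened under 6.16.2.2. The same 5 still counts as an outcome in the worst-score analysis (6.16.1.2), which runs from Day 1.

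**Illustration of size (all rates are assumptions).** Let both arms have true 21-day risk p. Let a fraction d of the active arm worsen after the infusion on Day 1 and be excluded as already worse at baseline, with none in the placebo arm. The observed active risk is (p − d)/(1 − d), its odds are (p − d)/(1 − p), and the observed odds ratio is (p − d)/p = 1 − d/p. The true value is 1.00.

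| p | d = 1% | d = 3% | d = 5% |
|---|---|---|---|
| 10% | 0.90 | 0.70 | 0.50 |
| 20% | 0.95 | 0.85 | 0.75 |
| 30% | 0.97 | 0.90 | 0.83 |

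At p = 20% the observed active risk is 19.2%, 17.5% and 15.8%. If d is the same in both arms, both observed risks are (p − d)/(1 − d) and the odds ratio stays at 1.00; events are lost but no difference is created.

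**The case against.** The strongest reply is that this is a wording slip with little reach, and much of that reply stands.

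- **Timing is unknown.** Neither document says that Day 1 vital signs or symptoms are taken after the infusion. The monitoring in protocol 6.1 looks for infusion reactions and is not stated to supply severity data. This stands: post-infusion values can become baseline, but it is not shown that they do.
- **Hidden harm.** A reader might infer that the rule conceals harm from the antibody. The documents do not support that. Safety has its own pre-dose baseline, hospitalizations are summarized and listed whatever the baseline (SAP 6.12.5), and hospitalization-or-death and deterioration still count a participant admitted hours after dosing. Protocol 2.3 gives no rate for early worsening and says its cause is unknown.
- **NIAID.** A reader might infer that such a participant can never count as worsened. That is too strong: any further decline counts, and only the Day 1 step is lost. Inpatients are excluded at entry (criterion 10), so a hospitalized baseline score would also be visibly odd.
- **Severity.** A fast pulse alone does not make a participant moderate; protocol Table 1 requires symptoms as well as signs.
- **Scope.** The two incidence objectives are listed only for the Part 1 Treatment population. SAP 6.10.3.1 speaks of Treatment populations in the plural, but by protocol 9.3 both arms of the Part 2 Treatment Cohort and of Part 3 receive LY3819253, so only Part 1 offers a placebo contrast.
- **Protocol latitude.** Protocol 9.4.1 allows for exceptions. It does not follow that an unexplained one is sound, least of all one at odds with two of the SAP's own tables.

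The conflict itself survives all of these.

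**Conclusion.** The point holds in a limited form. SAP 6.1.2 contradicts protocol 9.4.1 without giving a reason and does not fit SAP Tables PYAD.6.2 and PYAD.6.7. Followed as written, it can turn an unlabelled Day 1 post-infusion vital sign, symptom or lowest-of-day NIAID score into a baseline value. The possible damage is confined to the three exploratory analyses, and the two at-risk subsets matter essentially in the Part 1 Treatment population.

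The size cannot be read from the documents. The odds ratios of 0.50 to 0.97 rest on assumed risks, on every Day 1 worsening being captured as baseline, and on none occurring under placebo. They show what would be needed and are no evidence that bias exists. A spurious difference between arms requires Day 1 worsening to differ by arm. The trial's confirmatory conclusions are not at risk, but the correction is cheap enough to be worth making.

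**What to change.** In SAP 6.1.2, replace the date-based clause with *before the start (date and time) of study drug administration*, which restores the rule in protocol 9.4.1. Making the same change in the RT-PCR and serology sentence keeps the section consistent and alters nothing for scheduled samples.

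Add two rules:
- Take baseline NIAID from status before the infusion. No participant is an inpatient at entry, so an admission later on Day 1 then counts as post-baseline.
- Where a Day 1 vital sign or symptom has no recorded time, do not assume that it is post-dose. That would turn genuine pre-dose findings into false incident events and push baseline back to screening, up to 7 days earlier. Use the value as baseline in the main analysis, and add a sensitivity analysis using the screening value where there is one.

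The cost is SAP text and one extra exploratory run. Infusion start and end times are already recorded (protocol 8.5). The protocol does not specify clock times for vital signs or symptoms, so it should be checked whether the data capture system holds them. Sample size, visits and alpha are unchanged.

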8.1. Efficacy Assessments

8.1.1. SARS-CoV-2 Viral Swab and Serology

For details concerning viral swab, see Pharmacodynamics (Section 8.6). In Part 1, any positive result from a baseline SARS-CoV-2 test (NP or nasal swab) will result in the participant being declared SARS-CoV-2 positive in the analysis populations. In Part 2, the result from the screening POC test and baseline SARS-CoV-2 test are planned to be used to define SARS-CoV-2 status for the analysis populations.

Nasal swabs are planned during the evaluation and post-evaluation period at times described in the SoA. However, in the event nasal swabs cannot be supplied, the Sponsor may substitute with oropharyngeal, mid-turbinate or nasopharyngeal swabs. For instructions related to performing the nasopharyngeal, mid-turbinate, nasal, or oropharyngeal, swab, see guidance provided by Sponsor.

For Part 3, any positive result from a baseline SARS-CoV-2 test (NP) will result in the participant being declared SARS-CoV-2 positive in the analysis populations. NP swabs are planned during the evaluation and post-evaluation period at times described in the SoA.

For details concerning viral serology, see Pharmacodynamics (Section 8.6).

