#### 6.16.1.3. SARS-CoV-2 Clearance

For qualitative determination of viral clearance, the lab determination of “positive”/“negative” will be used. SARS-CoV-2 clearance (yes/no) is defined as a single negative RT-PCR test for the SARS-CoV-2 virus. The date of viral clearance is defined as the date of the first occurrence of a negative test.

The proportion of patients that achieve SARS-CoV-2 clearance within 1, 2, or 3 weeks of becoming SARS-CoV-2 positive will be summarized by treatment group in frequency tables and listed for the Prevention populations and the Part 1 Treatment population. Similar summaries will be made for the proportion of patients in the Part 2 Treatment and Part 3 treatment populations that achieve SARS-CoV-2 clearance within 8 and 29 days of becoming SARS-CoV-2 positive.

In addition, the number of patients that achieve SARS-CoV-2 clearance within 1, 2, or 3 weeks (or, for the Part 2 Treatment and Part 3 treatment populations, within 8 and 29 days) of becoming SARS-CoV-2 positive will be analyzed using logistic regression to compare treatment groups, if there are sufficient data available. Missing data will be imputed using the NRI method as described in Section 6.3.3. This comparison will be made on the Prevention and Treatment populations.

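### In Part 1, a participant positive only on the Day 1 nasopharyngeal swab is counted as cleared on a nasal negative, because the SAP's clearance rule matches neither specimen nor order

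*SAP*

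**What the plan says.** **Baseline status.** SAP 6.1.2: "A participant will be considered RT-PCR positive at baseline if any RT-PCR result is determined to be positive". Protocol 8.1.1 says the same for Part 1 and names the specimens: "any positive result from a baseline SARS-CoV-2 test (NP or nasal swab) will result in the participant being declared SARS-CoV-2 positive".

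**Swab schedule.** Protocol 1.3.1 covers Part 1 and the Part 2 Prevention Cohort. The row "SARS-CoV-2 nasopharyngeal swab (for PCR test) taken from both nostrils" is marked on Day 1 only. The row "SARS-CoV-2 nasal swab (for PCR test) taken from both nostrils" is marked on Day 1, at each weekly visit from Day 8 to Day 57, at early termination and on Day 85. Both Day 1 swabs are pre-dose. Protocol 8.1.1 confirms the follow-up specimen: "Nasal swabs are planned during the evaluation and post-evaluation period at times described in the SoA". It allows one exception: "in the event nasal swabs cannot be supplied, the Sponsor may substitute with oropharyngeal, mid-turbinate or nasopharyngeal swabs".

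**Clearance.** SAP 6.16.1.3: "SARS-CoV-2 clearance (yes/no) is defined as a single negative RT-PCR test for the SARS-CoV-2 virus". It is dated at the first negative. SAP 6.16.1.4 computes time to clearance as first negative date minus first positive date plus 1. The Part 1 Treatment population (baseline RT-PCR positive, serology negative) is included.

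**Viral load.** SAP 6.16.2.1 converts Ct to log10 viral load as (45 − Ct)/3.321928, assigns Ct 45 to a negative test, and adjusts for viral load at confirmed infection. It gives a rule for choosing the gene (N1, then N2) but none for choosing the specimen.

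**The concern.** Classifying a participant as infected on either of two swabs is reasonable. The difficulty comes when the next step looks for a negative on only one of them. A participant whose qualifying positive was the NP swab, and whose nasal swab was already negative before dosing, has nothing to clear on the specimen that is followed. The SAP still counts the next nasal negative as clearance.

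Three analyses in the Part 1 Treatment population are exposed: the proportion cleared, time to clearance, and change in viral load. Some reported clearances and declines could reflect the switch of specimen rather than an effect on infection, and a real difference between LY3819253 and placebo in clearance would be harder to see.

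**Working it through.** The plan states no figure for this point, so there is none to reproduce. The check applies the SAP's own rules to one type of participant and then to a group.

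**1. One participant, NP-positive and nasal-negative on Day 1, infection unchanged.**

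- *Day 1 nasal negative counts (literal reading).* Time to clearance = Day 1 − Day 1 + 1 = 1 day, so clearance precedes dosing.
- *Only later swabs count.* Clearance falls at the first later nasal negative. At the Day 8 visit this gives 8 − 1 + 1 = 8 days.

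The participant is counted as cleared under either reading.

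**2. Effect on clearance proportions.** Let x be the share of NP-only positives. It is the same in both arms in expectation, because it is fixed before dosing. Let c be true clearance by a given visit, and s the proportion of NP-only positives scored as cleared by then.

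- Observed proportion = (1 − x)c + xs
- Observed difference = (1 − x)(c_active − c_placebo) + x(s_active − s_placebo)

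In the limiting case s = 1 in both arms. The literal reading gives this exactly. If only later swabs count, it requires every NP-only positive to have had a nasal negative by that visit. The difference is then multiplied by (1 − x).

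For illustration, take true clearance at the first weekly assessment as 50% active and 30% placebo. These rates and x are assumptions; none is in the documents.

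| x | Active: (1 − x)50% + x | Placebo: (1 − x)30% + x | Difference |
|---|---|---|---|
| 0% | 50% | 30% | 20 points |
| 5% | 52.5% | 33.5% | 19 points |
| 10% | 55% | 37% | 18 points |
| 20% | 60% | 44% | 16 points |
| 30% | 65% | 51% | 14 points |

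**3. Effect on viral load.** If the NP swab supplies the starting value and the next nasal swab is negative (Ct 45, viral load 0), the recorded change is −(45 − Ct)/3.321928:

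| Day 1 NP Ct (assumed) | Recorded change, log10 |
|---|---|
| 25 | −6.02 |
| 30 | −4.52 |
| 35 | −3.01 |
| 40 | −1.51 |

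On a nasal-to-nasal basis the same participant goes from 0 to 0, a change of 0. For a participant positive on both swabs, an assumed Ct gap of 1, 2, 3 or 5 cycles between specimens contributes 0.30, 0.60, 0.90 or 1.51 log10.

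**4. Where the mismatch can arise.** Protocol 1.3.2 schedules NP swabs at every swab visit for the Part 2 Treatment Cohort and Part 3, so it does not arise there. Prevention-population participants are negative at baseline, so their first positive normally comes from a scheduled nasal swab. SAP 6.16.2.1, however, names no population. Part 2 participants who are POC-negative but baseline PCR-positive may stay on the Prevention schedule (Protocol 4.1.2), so the viral-load part of the problem could reach them. The clearance part does not, because they belong to neither the Prevention nor the Treatment populations.

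**The case against.** **A matched baseline already exists.** A nasal swab is taken on Day 1, and SAP 6.16.2.1 does not say that the NP value is used. A reader might infer that every change score compares NP with nasal. The documents do not support that: for anyone nasal-positive on Day 1 a like-for-like comparison is available. What stands is that the SAP does not require it, and that for NP-only positives no later nasal swab can match the qualifying positive.

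**Not every later swab need be nasal.** Substitution is allowed if nasal swabs cannot be supplied. This limits any claim that follow-up is always nasal, but substitution would add specimen mixing rather than remove it.

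**The literal Day 1 clearance may not be intended.** SAP 6.16.1.3 counts clearance from becoming positive, which suggests the negative comes later. Even so, the NP-only positive is then cleared at the first later nasal negative.

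**The arms are treated alike.** A reader might infer bias in favour of active treatment. Both randomised arms have the same swabs, so the expected effect on clearance is inflation in both and a diluted difference. For viral load, a roughly constant NP–nasal offset largely cancels from the treatment contrast, because the model adjusts for the starting value. The absolute decline is what suffers.

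**The dilution is a ceiling.** An NP-only positive caught early may turn nasal-positive and not be scored as cleared at that visit, and treatment could affect how often this happens. The factor (1 − x) is therefore the limiting case.

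**Nothing confirmatory depends on it.** This stands in full. The primary and key secondary endpoints use baseline RT-PCR-negative participants, clearance is exploratory, and viral load over time is an additional SAP analysis.

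**Conclusion.** The concern holds for the Part 1 clearance analyses. Either-specimen positivity at baseline, nasal follow-up as scheduled, and a clearance rule with no specimen match and no ordering together make an NP-only positive count as cleared without any change in infection. Clearance can be inflated in both arms and the between-arm difference diluted by up to the NP-only share. That share is not in the documents, so the real size is unknown. The range of 19 to 14 points for a true 20-point difference rests on assumed shares of 5% to 30%, assumed clearance rates and the limiting case.

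For viral load the conclusion is weaker. The starting specimen is unstated, so change scores can mix specimens, mainly distorting the absolute decline.

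The point is minor. It touches exploratory endpoints only and has no bearing on power, alpha or the prevention conclusions.

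**What to change.** In SAP 6.16.1.3, 6.16.1.4 and 6.16.2.1, for baseline-positive participants followed on the Part 1 and Prevention Cohort schedule, state that:

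- the Day 1 nasal swab is the virology baseline;
- clearance and viral-load change are analysed only in participants nasal-positive on Day 1;
- the clearing negative must come after the positive;
- the NP result is still used to assign the analysis population;
- NP-only positives are listed separately.

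This is a wording change and needs no new samples. The restriction uses only a pre-dose result, so the randomised comparison within the subset is preserved.

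The cost is a smaller exploratory set. The NP-only share is unknown and may not be trivial. As planned, Part 1 has about 1700 − 1300 = 400 participants outside the Prevention population, and these include serology-positives, so the Part 1 Treatment population is smaller than that. Losing 10% to 30% of it would be noticeable, which is why the excluded participants should be reported.
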